## Version 2 (24 September 2021)

This modification is considered to be substantial based on the criteria set forth in Article 10(a) of Directive 2001/20/EC of the European Parliament and the Council of the European Union.

Section # and Name	Description of Change	Brief Rationale	Substantial/ Non-substantial	
Section 1.1 Synopsis	The synopsis was revised to align with revisions in the CSP sections.	Revisions were made for consistency.	Non-substantial	
Section 1.2 Schema	The schema was revised to align with revisions in Sections 6.6.1 and 9.2.	Revisions were made for consistency.	Non-substantial	
Section 1.3 Schedule of Activities	In Table 2 and Table 3, ADA sample timepoints were revised.		Non-substantial	
	Table 2 and Table 3 were aligned with revisions in Sections 6.2.3, 6.5.1 (newly added) and 6.6.1.1.	Revisions were made for consistency.	Non-substantial	
Section 4.1 Overall Design	Part A and Part B were described in more detail and the number of participants to be enrolled was updated. The participants to be included in the analysis in Cohort B1 was clarified.	Amended in response to request from FDA.	Non-substantial	
Section 4.2.1 Rationale for Endpoints	Added text to clarify that the selection of the RP2D will be made by the Study Steering Committee, based on the OBD.	Amended in response to request from FDA.	Non-substantial	
Section 4.5 Study Stopping Criteria	The stopping criteria were expanded and described in more detail.	Amended in response to request from FDA.	Substantial	
Section 5.1 Inclusion criteria	Inclusion criterion 9 for Part A was modified to require that participants failed at least 2 prior lines of systemic therapy (instead of 2 prior lines of therapy) and received at least 3 cycles of anti-PD-1/PD-L1 based therapy (instead of 1 cycle)	Amended in response to request from FDA.	Substantial	

## **Overall Rationale for the Modification:**

Section # and Name	Description of Change	scription of Change Brief Rationale	
Section 6.1.1 Investigational Products	Added text to describe dosing criteria for Cycles $\geq 2$ .	d text to describe dosing ia for Cycles $\geq 2$ .Amended in response to request from FDA.	
Section 6.2.3 AZD7789 IV Bag or Syringe Preparation for IV Administration	Added text to clarify how participants will be monitored during and after infusions, on Cycle 1 Day 1 and for subsequent doses.	xo clarify howAmended in response towill be monitoredrequest from FDA.after infusions, onrv 1 and fordoses.	
Section 6.5.1 (Premedication)	This section was added to discuss premedication to be administered 30 minutes prior to each dose.	on was added to Amended in response to Su emedication to be request from FDA. see. Su	
Section 6.5.2 Rescue Medication (previously Section 6.5.1)	Table 12 was updated to include a reference to the text added in Section 6.5.1. In addition, existing text was updated for clarification.Revisions were made for consistency.		Non-substantial
Section 6.6.1 Starting Dose, Dose Escalation Scheme, and Stopping Criteria	Added text to explain that the planned dose levels may need to be adjusted depending on reported AEs and DLTs.Amended in response to request from FDA.		Substantial
Section 6.6.1.2 Modified Toxicity Probability Interval	Added text to specify that the posterior distribution for all dose levels is Beta(1+a, 1+b), where a and b are the number of participants with and without a DLT at the current dose level, respectively. The criteria for an unsafe dose level and dose escalation/de- escalation decision rules were adjusted.	Amended in response to request from FDA.	Substantial
Section 6.6.3 Definition of Dose-limiting Toxicity	The DLT evaluation period was changed from 21 to 28 days from the first dose of AZD7789 on Cycle 1 Day 1.	Amended in response to request from FDA.	Substantial
	Updated conditions to be considered as DLTs: Conditions for thrombocytopenia were updated and conditions for CRS were added.	Amended in response to request from FDA.	Substantial

Section # and Name	Description of Change Brief Rational		Substantial/ Non-substantial
Section 6.6.6 Definition of DLT- evaluable Participants	The definition for an evaluable participant was aligned with revised definition of the DLT evaluation period in Section 6.6.3.Revisions were made for consistency.		Substantial
Section 8.6.2.1 Tumor Tissue Samples	Table 18 was corrected to indicate that Cycle 1 Day 8 biopsy during Part B is not mandatory if medically 		Non-substantial
Section 9.2 Sample Size Determination	The total number of participants to be enrolled in the study and the number of participants to be enrolled in Part B were updated.Amended in response to request from FDA.		Substantial
Section 9.3 Populations for Analyses	In Table 21, the definition for an evaluable participant was aligned with revised definition of the DLT evaluation period in Section 6.6.3.	Revisions were made for consistency.	Substantial
Section 9.4.2.2 Secondary Endpoint(s)	It was clarified that, for progression-free survival, additional supportive/sensitivity analyses will be provided in the SAP.	Amended in response to request from FDA.	Non-substantial
Section 9.4.3.1 Maximum Tolerated Dose Evaluation	Changed the probability percentage for dose level considered to be unsafe.	Amended in response to request from FDA.	Substantial
Section 9.5 Interim Analyses	It was clarified that participants treated at the RP2D in Part A will be included in Cohort B1.	Amended in response to request from FDA.	Substantial
Section 9.5.1 Relapsed or Refractory cHL, Anti-PD-1/PD-L1 Exposed	Defined No-Go and false No-Go criteria.	Amended in response to request from FDA.	Substantial
Section 9.5.2 Relapsed or Refractory cHL, Anti-PD- 1/PD-L1-naïve	Defined No-Go and false No-Go criteria.	Amended in response to request from FDA.	Substantial

Section # and Name	Description of Change	Brief Rationale	Substantial/ Non-substantial
Appendix I	Added section for Cytokine Release Syndrome (CRS).	Amended in response to request from FDA.	Substantial
Appendix J	Added abbreviations to align with revisions.	Revisions were made for consistency.	Non-substantial
Throughout	Minor editorial and document formatting revisions.	Minor, therefore have not been summarized.	Non-substantial

4.5.7.2	Presentations	
4.5.8	Echocardiogram/Multiple-gated Acquisition Scan (ECHO/MUGA)	52
4.5.8.1	Definitions and Derivations	
4.5.8.2	Presentations	52
4.5.9	B-symptoms	52
4.5.9.1	Definitions and Derivations	52
4.5.9.2	Presentations	
4.5.10	Other Safety Assessments	
4.5.10.1	Definitions and Derivations	
4.5.10.2	Presentations	
5	INTERIM ANALYSES	
6	REFERENCES	
_		
7	ADDENINICES	56

LIST OF ABBREVIATIONS

Abbreviation or Specialized Term	Definition
AE	Adverse event
AESIs	Adverse event of special interest
ATC	Anatomical Therapeutic Chemical
BICR	Blinded independent central review
BMI	Body mass index
BOR	Best overall response
BSR	Baseline scaled ratio
CI	Confidence interval
COVID-19	Coronavirus disease 2019
CPS	Clinical Pharmacology Scientist
CRF	Case Report Form
CRR	Complete Response Rate
CSP	Clinical Study Protocol
CSR	Clinical Study Report
CTCAE	Common Terminology Criteria for AEs
CV	Coefficient of variation
DCO	Data cut-off
DLT	Dose-limiting toxicity
DoCR	Duration of Complete Response
DoR	Duration of Response
ECG	Electrocardiogram
ЕСНО	Echocardiogram
ECOG	Eastern Cooperative Oncology Group
FAS	Full analysis set
ICF	Informed consent form
imAE	Immune-mediated adverse event
IP	Investigational Product
IPD	Important Protocol Deviation
ITT	Intention-To-Treat
LLOQ	Lower limit of quantification
LRV	Lower reference value
LVEF	Left ventricular ejection fraction

MedDRA	Medical Dictionary for Regulatory Activities
MR	Minor response
MRI	Magnetic resonance imaging
MTD	Maximum Tolerated Dose
mTPI	Modified toxicity probability interval
MUGA	Multiple-gated acquisition scan
OAE	Other significant adverse events
ORR	Objective Response Rate
os	Overall Survival
PAVA	Pool adjacent violators algorithm
PD	Progressive Disease
PFS	Progression-free Survival
PK	Pharmacokinetics
PT	Preferred Term
QTcF	Corrected QT interval, using Fridericia's formula
RP2D	Recommended phase 2 dose
RECIL	Response-evaluation Criteria in Lymphoma
SAE	Serious adverse event
SAP	Statistical Analysis Plan
SD	Stable disease
SOC	System Organ Class
Std Dev	Standard deviation
TEAEs	Treatment emergent adverse events
TV	Target value
WHO	World Health Organization

AMENDMENT HISTORY

CATEGORY Change refers to:	Date	Description of change	In line with CSP?	Rationale
N/A	Click or tap to enter a date.	Initial approved SAP	N/A	N/A
Presentation	21 Jun 2024	Updated analysis sets in section 4.1.2	Yes	CSP updated to version 4.0
Presentation	21 Jun 2024	Timing of analysis changed in section 1	Yes	CSP updated to version 5.0
N/A	02 Jul 2024	New approved version 2.0	Yes	N/A
Presentation	25 Sep 2024	Updated tumor assessment visit window	Yes	Correction
N/A	25 Sep 2024	New approved version 3.0	Yes	N/A

1 INTRODUCTION

The purpose of this document is to give details for the statistical analysis of study D9571C00001. The Statistical Analysis Plan (SAP) should not be read in isolation but in conjunction with the Clinical Study Protocol (CSP) version 5 (dated 07 May 2024) for details of study conduct.

If there is a discontinuation of the study, with no subjects starting a cohort or a part of the study, then the summary or analysis specified in this SAP for that cohort or part of the study will not be presented. The final data cutoff for the end of study and final analysis will take place when the last subject completes the last study visit. Following the end of study, subjects may transition to the post-trial access program to order to provide continued access to sabestomig (AZD7789).

2 CHANGES TO PROTOCOL PLANNED ANALYSES

Not applicable.

3 DATA ANALYSIS CONSIDERATIONS

3.1 Timing of Analyses

There are multiple planned data cut-offs (DCOs) for this study, consisting of interim analyses, a primary analysis, and a final analysis. The timing of the interim analyses may be combined where appropriate.

Refer to Section 5 for further details of the planned interim analyses.

The data cut-off for the final analysis will be taken once the last participant has transitioned to the post-trial access program.

Analysis milestone	Timing
Interim Safety Analysis (Cohort B1 & Cohort B2)	After approximately participants have received the first dose at prior to data-cut off. For Cohort B1, participants treated at the RP2D in Part A will be included as part of the participants.
Efficacy Interim Analysis (Cohort B1)	After approximately participants in each respective cohort are included in the interim response-evaluable population.

	Subsequent interim analyses may be performed after every additional participants for Cohort B1 get included in the response-evaluable population.
Efficacy Interim Analysis (Cohort B2)	After approximately participants are included in the interim response-evaluable population. Subsequent interim analyses may be performed after every additional participants for Cohort B2 get included in the response-evaluable population.
Primary Analysis	At after the final enrolled participant received first dose of sabestomig.
Final Analysis	May be performed after the last participant begins treatment or when Astrazeneca stops the study, whichever occurs first.

3.2 Analysis Populations

All participants who receive any amount of study intervention will be included in the Safety analysis set. For the safety and PK analyses, participants will be classified according to dose level they actually received. For all efficacy analyses, and for baseline and demography, participants will be classified according to the dose they were assigned to (ie, the planned dose level).

The analysis sets will be summarized and any exclusions from analysis sets will be presented in data listings that will include:

- participants excluded from the analysis set and
- data excluded from any analysis (e.g.: data censored at time of intra-participant dose escalation).

The following populations are defined:

Table 1 Populations for Analyses

Population/Analysis set	Description	Endpoint/Output
Enrolled	All participants who sign the Informed Consent Form (ICF), or whose legally authorized representative sign the Informed Consent Form.	Disposition
Full/Safety	All participants who receive any amount of study intervention.	Exposure Safety Baseline and demography PK concentrations and parameters Listings PFS OS
ITT	Participants assigned to study intervention.	Sensitivity analyses
Interim safety	All participants who received the first dose at least CCI to data cut-off.	Safety at interim
DLT-evaluable	Participants enrolled in the dose escalation phase who have received sabestomig and completed the DLT evaluation period (defined as 28 days after the start of study intervention) or who experienced any DLT.	DLT
Response-evaluable	All dosed participants who had measurable disease at baseline.	ORR CRR BOR Duration of response Duration of complete response
Interim response- evaluable	All dosed participants who had measurable disease at baseline and received first dose at CCI prior to data cut-off.	Efficacy at interim
PK	All participants who received at least 1 dose of study intervention with at least 1 reportable concentration.	PK concentrations PK parameters
Pharmacodynamics	All participants who received at least 1 dose of study intervention with at least 1 reportable pharmacodynamic measurement.	Pharmacodynamic endpoints
Immunogenicity	All participants who received at least 1 dose of study intervention with at least 1 reportable immunogenicity measurement.	Immunogenicity endpoints

-ed 30

		•
Population/Analysis set	Description	Endpoint/Output

BOR: best overall response; CRR: Complete Response Rate; DLT: dose-limiting toxicity; DoR: Duration of Response; DoCR: Duration of Complete Response; ITT: Intention to Treat; ORR: Objective Response Rate; OS: Overall Survival; PFS: Progression-free Survival; PK: pharmacokinetic(s).

Assigned to study intervention will not include participants determined to be a screen failure.

Individual PK concentration and parameter data for any participants not included in the PK analysis set or excluded from the descriptive summary tables, figures, and/or inferential statistical analyses – eg, due to important protocol deviations that might affect PK – will be included in the listings and flagged with an appropriate footnote.

DoR is reported for the subset of participants with objective response.

DoCR is reported for the subset of participants with complete response.

Data summaries may be presented on more than one analysis population, as appropriate.

3.3 General Considerations

Unless stated otherwise, data will be presented by dose level in Part A and by cohort in Part B. For Cohort B1, participants treated at the recommended phase 2 dose (RP2D) in Part A will be included.

3.3.1 General Study Level Definitions

The general principles described below are followed throughout the study:

- Continuous endpoints will be summarized by the number of observations, mean, standard deviation (Std Dev), median, upper and lower quartiles (as applicable), minimum, and maximum. For data that requires log-transformation, it is more appropriate to present geometric mean, coefficient of variation (CV), median, minimum and maximum. Categorical endpoints are summarized by frequency counts and percentages for each category.
- If data are available for less than 3 participants, where presented, only minimum, maximum and number of observations will be presented.
- In general, summaries will be presented by study part and by dose level or cohort.
 Dose level groups with only single participant will only be listed.
- Unless otherwise stated, percentages will be calculated out of the analysis set total (excluding efficacy and exposure) and by dose level or cohort as appropriate.
 Percentages will not be presented for zero counts.

^a Legally authorized representative will be required to sign a statement of informed consent and informed assent from the participant (as appropriate) that meets the requirements of 21 CFR 50, local regulations, ICH guidelines Health Insurance Portability and Accountability Act requirements, where applicable, and the IRB/IEC or study center.

- ed. 3.0

- For continuous data, descriptive summary statistics (mean, median, standard deviation, standard error, confidence intervals) will be rounded to 1 additional decimal place compared to the reported data. Minimum and maximum are displayed with the same accuracy as the reported data.
- For categorical data, percentages are rounded to 1 decimal place.
- Time to event variables will be presented using the Kaplan-Meier (KM) methodology where appropriate, including median time calculated from the KM curves.
- For summaries at the participant level, all values will be included, regardless of whether they appear in a corresponding visit-based summary.
- SAS® version 9.4 (as a minimum) will be used for all analyses. The pharmacokinetic (PK) parameters of the serum concentration data for sabestomig will be derived using non-compartmental methods in Phoenix® WinNonlin® Version 8.3 or higher (Certara).
- Baseline is the last non-missing value obtained prior to the first dose/administration of any study treatment and any information taken after first dose/administration of study treatment is regarded as post-baseline information. If two visits are equally eligible to assess participant status at baseline (eg. screening and baseline assessments both on the same date prior to first dose/administration with no washout or other intervention in the screening period), the average is taken as the baseline value. For non-numeric laboratory tests (ie, some of the urinalysis parameters) where taking an average is not possible then the best value is taken as baseline as this is the most conservative. In the scenario where there are two assessments on Day 1 prior to first dose, one with time recorded and the other without time recorded, the one with time recorded is selected as baseline. Where safety data are summarized over time, study day is calculated in relation to date of first treatment. For assessments on the day of first dose where time is not captured, a nominal pre-dose indicator, if available, serves as sufficient evidence that the assessment occurred prior to first dose. Assessments on the day of the first dose where neither time nor a nominal pre-dose indicator are captured is considered prior to the first dose if such procedures are required by the protocol to be conducted before the first dose. If no value exists before the first dose/administration, then the baseline value is treated as missing.
- In all summaries, change from baseline endpoints will be calculated as the post-treatment value minus the value at baseline. The percentage change from baseline will be calculated as (post-baseline value baseline value) / baseline value × 100. For any endpoint subjected to log transformation, the change from baseline calculated and summarized on the log scale will be back-transformed and presented as a 'baseline scaled ratio' (BSR). Percentage change will be then calculated as (BSR 1) × 100.
- Unless stated otherwise, two-sided confidence intervals are produced at 95%.

– ed. 3.0

- For the purposes of summarizing safety data assessed at visits, in addition to baseline
 data, only on treatment data will be included in the summary tables. On treatment
 data will be defined as data after the first dose of IP and with assessment date up to
 and including the date of last IP + 90 days, and prior to the start of any subsequent
 cancer therapy.
- For efficacy assessments, figures may only be produced for dose levels or cohorts with more than 10 participants.

3.3.2 Visit Window

For safety and tumor assessments, visit windows are defined for any presentations that summarise values by visit. The following conventions apply:

For tumor assessments:

 The protocol assigned windows for tumor assessments will be used to assign the result to a particular visit.

For safety assessments:

- Visit windows will be exhaustive so that data recorded at any timepoint has the potential
 to be summarized. Inclusion within the visit window will be based on the actual date and
 not the intended date of the visit.
- All unscheduled visit data have the potential to be included in the summaries.
- The window for the visits following baseline will be constructed in such a way that the
 upper limit of the interval falls half way between the two visits (the lower limit of the
 first post-baseline visit is Day 2). If an even number of days exists between two
 consecutive visits then the upper limit is taken as the midpoint value minus 1 day.
- If treatment cycle delays are experienced, the planned dosing visit windows will be
 modified during the programming to anchor to the actual visit date where intervention
 was administered on to adjust for these treatment cycle delays. The same rules apply to
 safety visits of other types (non-dosing visits) where the safety visit is moved due to a
 treatment cycle delay.
- Visit windowing will be done separately for each assessment based on the schedule of events specific to that assessment. See Appendix B for details.
- For summaries showing the maximum or minimum values, the maximum/minimum value recorded on treatment will be used (regardless of where it falls in an interval).

- Listings should display all values contributing to a time point for a participant.
- For visit based summaries, if there are more than one value per participant within a visit window then the closest value to the scheduled visit date will be summarized, or the earlier, in the event the values are equidistant from the nominal visit date. If there is still a tie, preference to the nominal visit at which the results were reported at will be given. The listings will highlight the value for the participant that contributed to the summary table, wherever feasible. Note: in summaries of extreme values, all post baseline values collected will be used including those collected at unscheduled visits regardless of whether or not the value is closest to the scheduled visit date.
- For summaries at a participant level, all values will be included, regardless of whether they appear in a corresponding visit based summary, when deriving a participant level statistic such as a maximum.

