- e Participants with active hepatitis A, B, or C are excluded. Participants who have chronic hepatitis B and receiving suppressive antiviral therapy are allowed on study if ALT is normal and viral load is controlled; controlled hepatitis B viral load is defined as serum hepatitis B virus DNA < 100 IU/mL by PCR. Participants who have chronic hepatitis C are allowed to be enrolled if ALT is normal and hepatitis C virus RNA is undetectable by PCR, either spontaneously or in response to a successful prior course of antihepatitis C therapy.

- f A urine or serum pregnancy test is acceptable; if urine test is positive or equivocal, then serum  $\beta$ -hCG testing should be performed for confirmation.
- g For participants in mainland China only, samples will not be collected.
- h Recent biopsy within the last 4 months is required for participants in Part A mini-expansion and Part B unless medically contraindicated. Within that time period, participant must not have received any anti-cHL treatment since the last line of therapy, otherwise fresh tissue is required. For participants in Part A Dose Escalation, tumor tissues biopsy within prior 4 months is optional.
- i AstraZeneca may request prior images/scans performed up to 6 months prior to start of study intervention.

Clinical Study Protocol - Version 5 Sabestomig (AZD7789) - D9571C00001

Abbreviations: AE: adverse event; ALT: alanine transaminase; COVID-19: coronavirus disease 2019; ECG: electrocardiogram; FEV1: forced expiratory volume over 1 second; FVC: forced vital capacity; HIV: Human immunodeficiency virus; PCR: polymerase chain reaction; SAE: serious adverse event.

Study Period	Intervention Period							
Visit	V2	V3	V4	V5	V6	V7	V8-Vn	
Cycle Number and Day	C1D1	C1D3	C1D8	C1D15	C2D1	C2D8	C3D1-CnD1 a	
Procedure/Window			± 1 D	± 3 D	±1 D	± 3 D	± 3 D	
Abbreviated (symptom-directed) physical examination including weight (Section 8.2.2) b	Х		X	Х	X b	Х	X b	
12-lead ECG (triplicate) (Section 8.2.4) c	X °		X		X °	Х	C3D1 °, C4D1 °, and as clinically indicated thereafter	
Left ventricular ejection fraction by echocardiogram/ multiple-gated acquisition scan (Section 8.2.5) d	As clinically indicated							
Vital signs including pulse oximetry (Section 8.2.3) e	X °		Х	X	X e	Х	X °	
Eastern Cooperative Oncology Group performance status (Section 8.2.6)	х				Х		Х	

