#### Table 3Schedule of Activities for the Intervention Period (Part B Dose Expansion)

Study Period				Intervention Period		
Visit	V2	V3	V4	V5	V6	V7-Vn
Cycle Number and Day	C1D1	C1D8	C1D15	C2D1	C2D8	C3D1-CnD1
Procedure/Window		± 1 D	± 3 D	± 1 D	± 3 D	± 3 D
Abbreviated (symptom-directed) physical examination including weight (Section 8.2.2) a	Х	Х	X	X a	Х	X a
12-lead ECG (triplicate) (Section 8.2.4) b	X b	X b		Xb	X b	C3D1 b , C4D1 b , and as clinically indicated thereafter
Left ventricular ejection fraction by echocardiogram/ multiple-gated acquisition scan (Section 8.2.5) °	As clinically indicated					
Vital signs including pulse oximetry (Section 8.2.3) d	X d	X	X	X d	Х	X d
Eastern Cooperative Oncology Group performance status (Section 8.2.6)	Х			X		x
Assessment of B-symptoms (Section 8.1.1)	Х			Х		Х
Assessment of AEs/SAEs (Section 8.3)	←			XX		→
Concomitant medications (Section 6.5)	←			X		
Blood and Urine Tests for Safety	L					
Clinical Chemistry (Section 8.2.7) e	X f	Х	Х	Х		Х
Hematology (Section 8.2.7) e	X f	Х	Х	Х		X
Cardiac troponin (Section 8.2.7) e	If clinically indicated					
Glycated hemoglobin (Section 8.2.7)						C3D1, C5D1, C7D1, C9D1, C11D1, C13D1, C15D1, C17D1, C19D1, C21D1, C23D1, C25D1, C27D1, C29D1, C31D1, C33D1 and C35D1
Thyroid function (thyroid-stimulating hormone, free thyroxine, and free triiodothyronine as indicated g ; Section 8.2.7) e	X f		X	x		x

Table 3	Schedule of Activities for the Intervention Period (	(Part B Dose Expansion)
	Seneralie of 11000 101 0100 1000 1000 1000 100000 1000000	

Study Period	Intervention Period					
Visit	V2	V3	V4	V5	V6	V7-Vn
Cycle Number and Day	C1D1	C1D8	C1D15	C2D1	C2D8	C3D1-CnD1
Procedure/Window		± 1 D	± 3 D	± 1 D	± 3 D	± 3 D
Anti-thyroid antibodies (anti-thyroid peroxidase antibodies, thyroglobulin antibodies, thyrotropin receptor antibodies; Section 8.2.7)				As clinically indic	cated	
Coagulation parameters (Section 8.2.7) e	X f	Х	Х	Х		Х
Hepatitis B and C virology (Section 8.2.7) h						C5D1, C9D1, C13D1, C17D1, C21D1, C25D1, C29D1 and C33D1
Pregnancy test (urine or serum; women of childbearing potential only; Section 8.2.7) e	X f			х		X
Urinalysis (Section 8.2.7)	As clinically indicated					
Blood Tests for PK and Immunogenicity	·					

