Appendix B Time windows

B 1 Tumor assessments

Timepoint	Naming convention in outputs	Window
Screening	Screening	-28 – 1
At least 10 days after sabestomig administration in Cycle	CCI	CCI
At least 10 days after sabestomig administration in Cycle	CCI	CCI
At least 10 days after sabestomig administration in Cycle	CCI	CCI
1 year after date of first infusion	After 1 year	314 – 455 [a]
1 year and 6 months after date of first infusion	After 1.5 years	456 – 638 [a]
2 years after date of first infusion	After 2 years	639 – 821 [a]
2.5 years after date of first infusion	After 2.5 years	822 – 913 [a]
Q6M until EoS		

Any scan not within the above windows will be assigned to an unscheduled timepoint.

[a] If there are multiple scans in this period, the earliest scan will be assigned to the timepoint.

B 3 Time windows for Part A

	Window					
Visit	Hematology Chemistry	Physical examination Vital Signs	Coagulation	ECG	B-symptoms	Thyroid function
Cycle 1 Day 1	1	1	1	1	1	1
Cycle 1 Day 3	2-5					
Cycle 1 Day 8	6 - 11	2 - 11	2 - 11	2 - 15		
Cycle 1 Day 15	12 - 18	12 - 18	12 - 18			2 - 18
Cycle 2 Day 1	19 - 32	19 - 25	19 - 32	16 - 25	2 - 32	19 - 32
Cycle 2 Day 8		26 - 36		26 - 36		
Cycle 3 Day 1	33 - 53	37 - 53	33 - 53	37 - 53	33 - 53	33 - 53
Cycle 4 Day 1	54 - 74	54 - 74	54 - 74	54 - 74	54 - 74	54 - 74
Cycle 5 Day 1	75 - 95	75 - 95	75 - 95	75 - 95	75 - 95	75 - 95

Time windows for Part B B 3

	Window					
Visit	Hematology Chemistry	Physical examination Vital Signs	Coagulation	ECG	B-symptoms	Thyroid function
Cycle 1 Day 1	1	1	1	1	1	1
Cycle 1 Day 8	6 - 11	2 - 11	2 - 11	2 - 15		
Cycle 1 Day 15	12 - 18	12 - 18	12 - 18			2 - 18
Cycle 2 Day 1	19 - 32	19 - 25	19 - 32	16 - 25	2 - 32	19 - 32
Cycle 2 Day 8		26 - 36		26 - 36		
Cycle 3 Day 1	33 - 53	37 - 53	33 - 53	37 - 53	33 - 53	33 - 53
Cycle 4 Day 1	54 - 74	54 - 74	54 - 74	54 - 74	54 - 74	54 - 74
Cycle 5 Day 1	75 - 95	75 - 95	75 - 95	75 - 95	75 - 95	75 - 95

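### In SAP Appendix B the Part B hematology/chemistry window for Cycle 1 Day 8 starts at Day 6 instead of Day 2, so Days 2–5 fall in no window

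*SAP*

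**What the plan says.** SAP 3.3.2 (Visit Window) sets the rules for safety assessments:

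- "Visit windows will be exhaustive so that data recorded at any timepoint has the potential" to be summarized.
- The lower limit for the "first post-baseline visit is Day 2", and for later visits the "upper limit of the interval falls half way between the two visits".
- "Visit windowing will be done separately for each assessment based on the schedule of events specific to that assessment. See Appendix B for details".
- "All unscheduled visit data have the potential to be included in the summaries".
- When one window holds several values, the by-visit summary takes the one nearest the nominal day, and the earlier one if two are equally near. Maximum, minimum and participant-level summaries use every value, wherever it falls.

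The two parts have different visits. The header of Protocol Table 2 (Part A) reads "Cycle Number and Day C1D1 C1D3 C1D8 C1D15 C2D1 C2D8", and chemistry and hematology are drawn at C1D3. The header of Protocol Table 3 (Part B) reads "Cycle Number and Day C1D1 C1D8 C1D15 C2D1 C2D8 C3D1-CnD1", with no C1D3.

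SAP Appendix B gives the windows. In the Part A table, hematology/chemistry has Cycle 1 Day 3 = 2–5 and Cycle 1 Day 8 = 6–11. In the table headed "Time windows for Part B B 3" the Day 3 row is gone, but Cycle 1 Day 8 for hematology/chemistry is still 6–11. In that same row, physical examination/vital signs and coagulation are 2–11 and ECG is 2–15. Both tables end at Cycle 5 Day 1, Days 75–95.

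**The concern.** A lower limit of Day 6 is correct only when a Day 3 window precedes it. In Part B none does, so one printed cell contradicts two rules in the section that refers the reader to this appendix: that the windows are exhaustive, and that the first one starts on Day 2. A programmer must then choose between the table and the text. Two programmers could choose differently, and a check of the output against Appendix B alone would accept the wrong version.

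What is at stake is the by-visit presentation of Part B hematology and chemistry. Laboratory changes from baseline are among the Part B primary safety endpoints (Protocol Table 5). SAP 4.5.4.1 calculates change from baseline for each post-dose visit, and Protocol 9.4.3.3 foresees description of laboratory parameters over time.

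**Working it through.** **Inputs.** The window rules come from SAP 3.3.2, the visit days from Protocol Tables 2 and 3, and the printed windows from SAP Appendix B. With 3-week cycles, Cycle k Day 1 falls on Day 21(k−1)+1: Days 22, 43, 64, 85 and 106 for Cycles 2 to 6.

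**Formula.** First lower limit = Day 2. Upper limit = midpoint of two consecutive nominal days, with a half-day taken down. Next lower limit = previous upper limit + 1.

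**Step 1: reproduce Part A hematology/chemistry** (Days 3, 8, 15, 22, 43, 64, 85).

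| Visit | Midpoint with next visit | Window by rule | Printed |
|---|---|---|---|
| C1D3 | (3+8)/2 = 5.5 | 2–5 | 2–5 |
| C1D8 | (8+15)/2 = 11.5 | 6–11 | 6–11 |
| C1D15 | (15+22)/2 = 18.5 | 12–18 | 12–18 |
| C2D1 | (22+43)/2 = 32.5 | 19–32 | 19–32 |
| C3D1 | (43+64)/2 = 53.5 | 33–53 | 33–53 |
| C4D1 | (64+85)/2 = 74.5 | 54–74 | 54–74 |
| C5D1 | (85+106)/2 = 95.5 | 75–95 | 75–95 |

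All seven match. The rule also reproduces the other five Part A columns.

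**Step 2: Part B hematology/chemistry** (same days without Day 3). C1D8 is now the first post-baseline visit, so its lower limit is Day 2. Its upper limit is still 11.5 taken down to 11. The rule gives **2–11**; the table prints **6–11**. Days 2, 3, 4 and 5 are uncovered, which is 4 of the 10 days the window should hold. Every other Part B window matches the rule. Part B coagulation, drawn at the same visits, is printed as 2–11.

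**Step 3: the clause on an even number of days.** SAP 3.3.2 adjusts the midpoint in that case, and the clause can be read in two ways. For hematology/chemistry, consecutive visits in Part B are 7 or 21 days apart, so every midpoint is a half-day and both readings give 2–11. The alternative reading would move only some ECG and physical examination/vital signs limits.

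**Step 4: when the cell matters.** The scheduled Part B C1D8 draw has a ±1 day window, so it falls on Days 7–9, at most 1 day from nominal. A sample on Days 2–5 is 6, 5, 4 or 3 days from nominal. With the window corrected to 2–11:

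- a Day 2–4 sample (4 to 6 days away) loses to any value on Days 6–11 (at most 3 days away);
- a Day 5 sample (3 days away) loses to any value on Days 6–10 (at most 2 days away) and ties with Day 11, where the earlier value is taken.

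So the correction changes a by-visit result only for a participant with a Day 2–5 sample and no value nearer to Day 8.

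**Step 5: after Cycle 5.** The same rule gives C6D1 (Day 106) = Days 96–116, then a window of −10 to +10 days around each Cycle k Day 1. Cycle 35 Day 1 is Day 21×34+1 = 715, so its window is 705–725. On-treatment data run to last dose + 90 days, at most Day 715+90 = 805 without delays.

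**The case against.** The strongest reply is that the slip is almost without consequence. By the nearest-value rule, a scheduled Day 7–9 draw would displace a Day 2–5 sample even in a correct window. Worst-grade and Grade 3 or higher outputs (SAP 4.5.4.2) do not use these windows, and the by-visit laboratory display named there is an optional graph. All of this stands and limits the point to a consistency correction. It does not make the printed cell right.

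A reader might infer three stronger things that the documents do not support:

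- **That early chemistry drawn for a suspected first-dose reaction is lost from Part B safety results.** It stays in the extreme-value and participant-level summaries and in the listings. In most cases the scheduled draw would be chosen over it in the by-visit summary anyway. The reason for drawing such samples is also a supposition.
- **That disagreement between by-visit and worst-value summaries is a defect.** SAP 3.3.2 intends participant-level and extreme-value summaries to use values that the by-visit summary does not select. This remains so after the fix.
- **That data after Day 95 are excluded.** The printed rows do omit Cycles 6–35, which is 35−5 = 30 dosing visits. But the midpoint rule generates those windows, SAP 3.3.2 provides for re-anchoring after cycle delays, and nothing says later data are dropped. This is missing detail, not a contradiction.

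**Conclusion.** The point holds as a minor, certain error in one cell. The Part B hematology/chemistry window for Cycle 1 Day 8 should be 2–11, not 6–11. As printed, Days 2–5 fall in no window for those two panels, contrary to SAP 3.3.2. The other five Part B columns have no gap up to Day 95.

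The practical effect is small: it is confined to by-visit hematology and chemistry summaries, for participants with a Day 2–5 sample and no value nearer to Day 8. The documents give no basis for estimating how many participants that would be. The conclusion assumes that Appendix B is applied as printed and that Part B safety laboratories follow Protocol Table 3. The extra 48-hour sample for mainland China in that table is for PK and creates no Day 3 safety visit.

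The stop at Cycle 5 is a secondary note on completeness and does not carry the point.

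**What to change.** In the Part B table of SAP Appendix B, change hematology/chemistry Cycle 1 Day 8 from 6–11 to 2–11, matching the coagulation column.

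To complete the appendix, add below Cycle 5 in both tables: for assessments scheduled every cycle, Cycle k Day 1 = Day 21(k−1)+1, window −10 to +10 days, through Cycle 35. Add windows for end of treatment and for the Day 30 and Day 90 follow-up visits. A line ending at Cycle 35 would not cover these, and they matter for anyone who stops early; the follow-up visits are dated from the last dose. The two safety tables share the number B 3, which can be corrected at the same time.

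The cost is one cell, one continuation line and the end-of-treatment and follow-up entries. No change to the protocol, data collection or patient management is needed.
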